4.7 PRODUCT ACCOUNTABILITY

In accordance with regulatory requirements, study sites must document the amount of investigational product (IP) received from and returned to the sponsor, and the amounts of IP dispensed to study subjects, and the amount returned by study subjects. Product accountability records must be maintained throughout the course of the study.

4.8 CONCOMITANT MEDICATION AND THERAPIES

All concomitant medications taken during the study and relevant procedures will be recorded on the eCRF.

Ongoing immunosuppressive therapy with steroids $\leq 10 \text{ mg/day}$ is permitted and must be documented in the source documentation and eCRFs.

Subjects will be counseled to avoid non-prescribed medicines or complementary alternative medicines excluded by the study. All medications a subject receives from the signing of the ICF through the 28-Day Follow-Up visit will be documented.

After discontinuation of study drug, any medication used in response to an AE is to be recorded on the appropriate eCRF.

The concomitant medication names will be coded by the sponsor according to the World Health Organization Drug Dictionary and classified by anatomical therapeutic chemical categories

4.9 CYP3A4 INHIBITORS/INDUCERS

CYP3A4 inhibitors/inducers should be used with caution.

4.10 DRUGS PROLONGING THE OTC INTERVAL

Subjects on concomitant medications known to have the potential for QTc prolongation will be excluded.

Kadmon Corporation, LLC

4.11 OVERDOSE

Doses of belumosudil considered to represent an overdose have not been defined. In clinical studies of belumosudil, repeat dosing of 500 mg BID for 28 days was generally well tolerated in healthy volunteers. There are no known antidotes to belumosudil, and no specific treatment is recommended in the event of a suspected overdose. The treating Investigator should employ clinical judgment in managing subjects with suspected overdose. Overdose should be reported as an AE.

4.12 DOSE MODIFICATION GUIDELINES

Any clinically significant toxicity will necessitate consideration of either a pause or cessation of therapy. Dose modification of therapy is permitted in the open label phase as outlined in Table 5.Guidelines for management of treatment-emergent toxicities in subjects receiving belumosudil are outlined in Table 3Error! Reference source not found..

Table 3 Guidelines for Management of Treatment-emergent Toxicities (Double-blinded Phase)

Toxicity	Recommended Action
Grade \geq 3 LFTs (AST,	Complete the "Treatment-emergent LFT elevations" eCRF
ALT or total bilirubin)	Discontinue belumosudil
Other Grade ≥ 3	Discontinue belumosudil
clinically significant	
toxicities considered	
related to belumosudil	
Grade 2 clinically	Consider pause or cessation of therapy
significant toxicities	Dose interruption for toxicity will be permitted up to 14 days.
	• If toxicity does not resolve to Grade 1 or below for 14 days, subjects
	will be discontinued from treatment

ALT = alanine aminotransaminase; AST = aspartate aminotransaminase; eCRF = electronic case report form; LFT = liver function tests

Table 4 Guidelines for Management of Treatment-emergent Toxicities (Open-Label Phase)

(Open-Laber I hase)	
Toxicity	Recommended Action
Grade ≥ 3 LFTs (AST, ALT or total bilirubin)	Complete the "Treatment-emergent LFT elevations" eCRF Discontinue belumosudil
Other Grade ≥ 3 clinically significant toxicities considered related to belumosudil	Discontinue belumosudil
Grade 2 clinically significant toxicities	 Consider pause or dose modification(table 5) of therapy Dose interruption for toxicity will be permitted up to 14 days. If toxicity resolves to grade 1 or below then consider resuming belumosudil at current dose or one dose decrement as outlined in Table 5 below If toxicity recurs, hold dose as above then consider resuming belumosudil at one dose decrement If toxicity does not resolve to Grade 1 or below for 14 days, subjects will be discontinued from treatment

ALT = alanine aminotransaminase; AST = aspartate aminotransaminase; eCRF = electronic case report form; LFT = liver function tests

Dose interruption for toxicity management for 14 days is permitted. Subjects requiring pauses of more than 14 days will be discontinued from the study unless approved by the Medical Monitor.

Table 5. Belumosudil Dose Decrements

Belumosudil Dose	Dose Reduction
200 mg BID	200 mg QD
200 mg QD	200 mg QOD

BID = twice daily; QD = once daily; QOD = once every other day

Kadmon Corporation, LLC

If the reduced dose is tolerated for 1 complete cycle, the dose may be escalated to the previous dose.

5. STUDY ASSESSMENTS AND PROCEDURES

The schedule of assessments is outlined in Error! Reference source not found.

CRISS assessments will not be performed on site in either the Double-blind or Open-label Periods, but rather will be calculated outside of EDC.

5.1 SCREENING PERIOD (DAY -29 TO -1)

Informed consent must be obtained before any study-specific samples are taken or study-specific tests or evaluations are conducted. The following assessments at the screening visit are to occur within 29 days of first dose of study drug (Week 1, Day 1 visit). Study eligibility will be based on satisfying all the study inclusion and exclusion criteria.

At the screening visit, information will be collected and subjects will have clinical evaluations as follows:

- Informed consent
- Subject demography
- Medical history
- Inclusion/exclusion criteria
- mRSS
- FVC
- Complete PE
- Vital signs
- Weight
- Hematology and chemistry
- 12-lead ECG
- Pregnancy test
- Concomitant medication assessment
- AE assessment

5.2 DOUBLE-BLINDED TREATMENT PERIOD

After completion of screening procedures and confirmation of subject eligibility, the subject will be randomized and enrolled into the study. Subjects who are enrolled into the study are to undergo all subsequent evaluations required by the protocol.

5.2.1 Week 1, Day 1 Visit (Baseline)

At the Week 1 Day 1 visit, subjects will come to the clinic to have the following procedures:

- Confirmation of inclusion/exclusion criteria
- Randomization
- mRSS
- SHAQ-DI
- Physician Global Assessment
- Patient Global Assessment
- Pulmonary function test (PFT)*
- HRCT (± 7 days; for subjects with ILD at screening only)
- Skin biopsies
- Sampling for PD
- Complete PE
- Vital signs
- Weight
- Hematology and chemistry*
- Urinalysis*
- 12-lead ECG
- Pregnancy test
- Dispense study diary
- Study drug administration review with patient
- Dispense study drug
- Concomitant medication assessment
- AE assessment

*If these assessments were conducted within seven (7) days of baseline, they do not need to be repeated.

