Pregnancy Test ^k	X	X	X	X	X	X	X	X	X	X	X	X	X	X	X	X	X	X
Study diary (dispense/collect)		х		х	х	Х	Х	Х	Х	Х	х	х	Х	х	Х	х		х
Study drug administration ¹		х	X	x	x	x	x	х	Х	Х	х	х	Х	х	Х			х
Dispense/Collect study drug ¹		х		х	х	х	х	х	X	X	х	х	X	х	X	x		х
Concomitant																		

Abbreviations: CRISS = Combined Response Index in Diffuse Cutaneous Systemic Sclerosis; ECG = electrocardiogram; EDC = electronic data capture; EOT = End-of-Treatment; FVC = forced vital capacity; HRCT = high-resolution computerized tomography; ICF = informed consent form; ILD = interstitial lung disease; mRSS = modified Rodnan Skin Score; PE = physical examination; PFT = pulmonary function test; SHAQ—DI = Scleroderma Health Assessment Questionnaire—Disability Index

The ICF must be signed before any study procedure begins.

Medications

Adverse Events

Kadmon Corporation, LLC

Page 86 of 99

27 May 2021

To be collected from the date that the ICF is signed until 28 days after last dose of Belumosudil.

[figure not shown]
- b. Re-randomization of the placebo group to one of two arms will take place after the un-blinding procedures take place.
- c. CRISS will not be performed on site, but rather will be calculated outside of EDC.
- d. mRSS, SHAQ-DI, FVC, physician global assessment and patient global assessment will be performed at baseline Day 1, Day 57, Day 113, Day 169, Day 197, and then every 8 weeks thereafter until Week 52. In addition, after their last dose of study drug (4-Week Follow-Up Visit). mRSS and FVC will also be performed at screening as one of the inclusion criteria. FVCs should be performed if PFT is not performed at the same visit.
- e. HRCT and PFTs, to include FEV₁, FVC, DL_{CO} (corrected for Hb), TLC, and RV, will be performed at baseline, Day 169, and Day 365 (each ± 7 days). In addition, PFTs will be performed after their last dose of study drug (4-Week Follow-Up Visit). If the HRCT or PFTs is performed within one month of the EOT visit, it does not need to be done again at the EOT visit.
- f. HRCT will be done only in subjects at Day 1, Day 169, and Day 365 (each ± 7 days) if they have confirmed ILD at baseline. This is not required at the End of Treatment visit.
- g. Double punch Skin biopsies are MANDATORY for all subjects on Day 1 and Day 169 and Optional on Day 365 and will be obtained from the dorsal mid-forearm for Gene Profiling. This assessment is not required for End of Treatment.

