3.1.6 Baseline

Baseline value is defined as the valid and last non-missing value obtained within 29 days prior to subject receiving the first study medication, unless otherwise stated under the related assessment section. Baseline can be the day before the first study medication or on the same day as the first study medication if a pre-dose assessment is available. Subjects without data on a parameter before the first study medication will have a missing baseline for this parameter.

For patients who randomized in placebo group in double blinded period and re-randomized in open label period, the baseline value of open label period is defined as the valid and last non-missing value obtained prior to subject receiving the first dose of belumosudil.

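### A baseline HRCT, or FEV1, DLco, TLC or RV, measured on Study Days 2–8 is allowed by the protocol but becomes a missing baseline under the SAP

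*Protocol*

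**What the plan says.** **Protocol, timing of the baseline assessments.** Section 5.2.1 lists "HRCT (± 7 days; for subjects with ILD at screening only" among the Week 1, Day 1 procedures. In Appendix A, footnote e says that HRCT and PFTs "will be performed at baseline, Day 169, and Day 365 (each ± 7 days", and footnote f says "HRCT will be done only in subjects at Day 1, Day 169, and Day 365 (each ± 7 days) if they have confirmed ILD at baseline". None of these limits the window to the days before dosing.

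The PFT line in section 5.2.1 has no ± window. It carries only an asterisk: "If these assessments were conducted within seven (7) days of baseline, they do not need to be repeated".

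Section 5.1 ties screening to the period "within 29 days of first dose of study drug (Week 1, Day 1 visit", which fixes first dose at the Day 1 visit. It lists mRSS and FVC at screening, but neither HRCT nor a full PFT.

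**SAP, definition of baseline.** Section 3.1.6 takes "the valid and last non-missing value obtained within 29 days prior to subject receiving the first study medication". A same-day value counts only when it was taken before dosing: "on the same day as the first study medication if a pre-dose assessment is available". Otherwise: "Subjects without data on a parameter before the first study medication will have a missing baseline for this parameter". The section lets an individual assessment section state a different rule. Neither 3.8.2.2 (PFTs) nor 3.8.2.6 (HRCT) does so. Both plan change from baseline: between groups for HRCT, and as summaries in subjects with ILD for the full PFT panel.

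**The concern.** A site that scans on, say, Day 5 has followed the protocol, yet the SAP treats that scan as post-baseline and leaves the subject without a baseline. The Week 24 scan then has nothing to be compared with. For a subject randomized to belumosudil, neither does the Week 52 scan.

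Change in lung fibrosis on HRCT is a named secondary objective, and only subjects with ILD contribute to it, in a trial with 20 subjects per arm. Neither the HRCT section nor the summaries of the other PFT parameters provide imputation, so a missing baseline removes the subject from the analysis. Without a stated rule, the programmer must either discard compliant data or choose a rule after the data are visible.

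**Working it through.** The plan states no figure on this point, so there is nothing to reproduce. The check compares the two rules by day count and then looks for a fallback.

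**1. Days in the window.** Inputs: Day 1 ± 7 days (Protocol 5.2.1; Appendix A, footnotes e and f), first dose on Day 1 (Protocol 5.1), and no Day 0 (SAP 3.1.5).
- Before Day 1: Study Days −7 to −1 = 7 days, all valid under SAP 3.1.6.
- Day 1 = 1 day, valid only if pre-dose.
- After Day 1: Study Days 2 to 8 = 7 days, none valid.
- Total 7 + 1 + 7 = 15 days. Share after the day of first dose: 7/15 = 46.7%.

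**2. Is another pre-dose value scheduled?** Inputs: Protocol 5.1 and the Appendix A schedule.

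| Parameter | Scheduled at screening | Result if the baseline test is done on Days 2–8 |
|---|---|---|
| HRCT | No | Baseline missing |
| FEV1, DLco, TLC, RV | No | Baseline missing |
| FVC | Yes | Screening value used |

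FVC enters the CRISS formula (SAP 3.8.1); FEV1, DLco, TLC, RV and HRCT do not. The score therefore keeps the baseline it needs.

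**3. What a missing baseline removes.** SAP 3.1.6 gives re-randomized placebo subjects a second baseline, the last value before their first belumosudil dose. Their Week 24 scan can fill that role, so their open-label change survives. Their double-blind change does not, and that is the change the placebo comparison needs.

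**4. Illustrative size.** The documents give neither the ILD share at entry nor the share of late scans. Both are assumed here: ILD share p from 20% to 60%, late share q from 10% to 7/15 (the latter if timing were uniform over the window). Baselines lost = 60 × p × q.
- Low: 60 × 0.20 = 12 subjects (4 per arm); 12 × 0.10 = 1.2 lost.
- Middle: 60 × 0.40 = 24 (8 per arm); 24 × 0.25 = 6.0 lost, or 2 per arm.
- High: 60 × 0.60 = 36 (12 per arm); 36 × 7/15 = 16.8 lost, or 5.6 per arm, leaving 12 − 5.6 = 6.4 per arm.

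**5. After reconciliation.** With a pre-dose-only window, none of the permitted days would follow first dose. With a stated SAP exception, every scan within the protocol window could serve as a baseline.

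**The case against.** The best case for leaving the plan alone has four parts.

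- **The PFT window is doubtful.** Section 5.2.1 puts the PFT at the Day 1 visit, and its asterisk reads most naturally as looking back from that visit. So does the closing note in Appendix A about screening completed within 7 days of baseline. Only footnote e gives PFTs a forward window. This stands: the PFT part rests on that footnote alone, and the HRCT part is firmer.
- **Earlier imaging may exist.** Subjects who are scanned have confirmed ILD, and the SAP lists an ILD diagnosis date. A clinical scan within 29 days before first dose could serve as baseline if it were captured. This stands as a possibility, but the protocol schedules no such scan.
- **Nothing shows that any scan would be late.** Correct. The 60% figure in Protocol 1.1 is also an upper bound on patients with systemic sclerosis who ever develop ILD. This trial requires disease duration of at most 5 years and excludes low FVC, so 12 per arm should not be read as an expected number.
- **Little depends on it.** HRCT is a categorical secondary measure in an exploratory study not sized by hypothesis testing. This limits the importance but does not remove the conflict.

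A reader might infer that FVC, and with it the primary endpoint, also loses baselines. The documents do not support that. Screening FVC is required (Protocol 5.1; Appendix A, footnote d) and FVC is part of eligibility, so a compliant subject always has a pre-dose value. That value may be up to 29 days old, while the patient and physician global assessments and SHAQ-DI are first scheduled on Day 1, but SAP 3.1.6 accepts it. A special FVC rule that put the pre-dose value first would change nothing.

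**Conclusion.** The conflict is real and narrow. As written, a protocol-compliant HRCT from Study Days 2–8 gives no baseline, and by footnote e the same holds for FEV1, DLco, TLC and RV. A scan on Day 1 after dosing also fails. Scans from Day −7 to pre-dose Day 1 are unaffected.

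The consequence is confined to the HRCT secondary endpoint and the PFT summaries in subjects with ILD. The number affected is unknown; the range of about 1 to 17 depends entirely on the two assumed shares and is not a forecast. The conclusion assumes that sites use the later half of the window at least sometimes and that no unscheduled pre-dose scan is available. It is a minor point, worth settling because it is cheap to settle before database lock.

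**What to change.** In SAP 3.8.2.2 and 3.8.2.6, using the exception that 3.1.6 already allows, add a rule such as:

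> For HRCT, FEV1, DLco, TLC and RV, baseline is the last pre-dose value. If there is none, baseline is the earliest value within the protocol window, through Study Day 8. Such baselines are flagged, and a sensitivity summary excludes the subjects concerned.

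The order matters. A rule that took the value closest to first dose would let an on-treatment Day 2 test displace a valid test from Day −6. FVC needs no special rule.

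For any subjects not yet enrolled, reconcile the protocol's baseline window with the SAP's pre-dose definition, and make the PFT line in section 5.2.1 agree with footnote e. The SAP rule is still needed for scans already taken, because a later change to the protocol window cannot recover them.

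The cost is one SAP rule, one flag and one extra summary. The downside is that a few baselines will follow up to a week of study drug; the flag and the sensitivity summary make their influence visible.

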5.2.2 Day 15 (\pm 3 Days) Visit

Subjects will come to the clinic to have the following procedures:

- Symptom-directed PE
- Vital signs
- Weight

- Hematology and chemistry
- Urinalysis
- 12-lead ECG
- Pregnancy test
- Study drug administration
- Concomitant medication assessment
- AE assessment

5.2.3 End of Week 4, Day 29 (\pm 3 Days) Visit

Subjects will come to the clinic to have the following procedures:

- Sampling for PK
- Symptom-directed PE
- Vital signs
- Weight
- Hematology and chemistry
- Urinalysis
- 12-lead ECG
- Pregnancy test
- Dispense and collect study diary
- Study drug administration
- Dispense & collect study drug
- Concomitant medication assessment
- AE assessment

5.2.4 End of Week 8, Day 57 (\pm 3 Days) Visit

Subjects will come to the clinic to have the following procedures:

- CRISS
- mRSS
- FVC
- SHAQ-DI
- Physician Global Assessment
- Patient Global Assessment
- Sampling for PK
- Sampling for PD

- Symptom-directed PE
- Vital signs
- Weight
- Hematology and chemistry
- Urinalysis
- 12-lead ECG
- Pregnancy test
- Dispense and collect study diary
- Study drug administration
- Dispense and collect study drug
- Concomitant medication assessment
- AE assessment

5.2.5 End of Week 12, Day 85 (± 3 Days) Visit

Subjects will come to the clinic to have the following procedures:

- Symptom-directed PE
- Vital signs
- Weight
- Hematology and chemistry
- Urinalysis
- 12-lead ECG
- Pregnancy test
- Collect and dispense study diary
- Study drug administration
- Collect and dispense study drug
- Concomitant medication assessment
- AE assessment

5.2.6 End of Week 16, Day 113 (\pm 3 Days)

Subjects will come to the clinic to have the following procedures:

- CRISS
- mRSS
- FVC
- SHAQ-DI

- Physician Global Assessment
- Patient Global Assessment
- Symptom-directed PE
- Vital signs
- Weight
- Hematology and chemistry
- Urinalysis
- 12-lead ECG
- Pregnancy test
- Collect and dispense study diary
- Study drug administration
- Collect and dispense study drug
- Concomitant medication assessment
- AE assessment

5.2.7 End of Week 20, Day 141 (\pm 3 Days)

Subjects will come to the clinic to have the following procedures:

- Symptom-directed PE
- Vital signs
- Weight
- Hematology and chemistry
- Urinalysis
- 12-lead ECG
- Pregnancy test
- Collect and dispense study diary
- Study drug administration
- Collect and dispense study drug
- Concomitant medication assessment
- AE assessment

5.2.8 End of Week 24, Day 169 (± 3 Days)

Subjects will come to the clinic to have the following procedures:

• CRISS

- mRSS
- FVC (if PFT not performed at visit)
- SHAQ-DI
- Physician Global Assessment
- Patient Global Assessment
- PFTs (\pm 7 days)
- HRCTs (± 7 days)
- Skin biopsies
- Sampling for PD
- Complete PE
- Vital signs
- Weight
- Hematology and chemistry
- Urinalysis
- 12-lead ECG
- Pregnancy test
- Collect and dispense study diary
- Study drug administration
- Collection and dispense study drug
- Concomitant medication assessment
- AE assessment

5.2.9 End of Double-Blinded Treatment Visit (End of Week 28, Day 197 [± 3 Days])

Subjects will come to the clinic to have the following procedures completed:

- Randomization (for subjects who had been receiving placebo [Group 3] to 1 of 2 treatments with belumosudil)
- CRISS
- mRSS
- FVC
- SHAQ-DI
- Physician Global Assessment
- Patient Global Assessment

- Complete PE
- Vital signs
- Weight
- Hematology and chemistry
- Urinalysis
- 12-lead ECG
- Pregnancy test
- Dispense and collect study diary
- Study drug administration
- Collect and dispense study drug
- Concomitant medication assessment
- AE assessment

5.3 OPEN-LABEL VISITS EVERY 4 WEEKS (± 3 DAYS) UNTIL WEEK 52

After 28 weeks of blinded treatment, subjects will continue on open-label treatment for 24 weeks. All subjects will return to the clinic every 4 weeks. Until Week 52, subjects will have safety assessments every 4 weeks and efficacy assessments every (8 weeks) as follows:

Every 4 weeks, subjects will have the following safety assessments, i.e., End of Week 32, Week 36, Week 40, Week 44, and Week 48.

- Symptom-directed PE (at Week 32, Week 36, Week 40, Week 44, and Week 48 visits)
- Vital signs
- Weight
- Hematology and chemistry
- Urinalysis
- 12-lead ECG
- Pregnancy test
- Collect and dispense study diary
- Study drug administration
- Collect and dispense study drug
- Concomitant medication assessment
- AE assessment

Page 49 of 99

27 May 2021

Every 8 weeks, subjects will have the following efficacy assessments, i.e., End of Week 36 (Day 253 \pm 3 days) and Week 44 (Day 309 \pm 3 days):

- CRISS
- mRSS
- FVC
- SHAQ-DI
- Physician Global Assessment
- Patient Global Assessment

END OF TREATMENT OR WEEK 52, (DAY 365 $[\pm 3 \text{ DAYS}]$)

Subjects who complete Week 52 the study will have the following procedures:

- CRISS
- mRSS
- FVC (if PFT not performed at visit)
- SHAQ-DI
- Physician Global Assessment
- Patient Global Assessment
- PFTs (\pm 7 days)
- HRCT (\pm 7 days)
- Skin biopsies (optional)
- Sampling for PD
- Complete PE
- Vital signs
- Weight
- Hematology and chemistry
- Urinalysis
- 12-lead ECG
- Pregnancy test
- Collect study diary
- Collect study drug
- Concomitant medication assessment
- AE assessment

Kadmon Corporation, LLC

Subjects who discontinue from the study prior to Week 52 will have the same assessments performed as subjects who complete Week 52.

5.5 28-DAY FOLLOW-UP VISIT

Subjects will return to the clinic twenty-eight (28) days (\pm 3 days) after their last dose of study drug. At this visit, the following procedures will be completed:

- CRISS
- mRSS
- SHAQ-DI
- Physician Global Assessment
- Patient Global Assessment
- PFT
- Complete PE
- Vital signs
- Weight
- Hematology and chemistry
- Urinalysis
- 12-lead ECG
- Pregnancy test
- Concomitant medication assessment
- AE assessment

5.6 UNSCHEDULED VISIT

For subjects requiring an unscheduled visit, the following procedures may be performed at the Investigator's discretion:

- CRISS
- mRSS
- FVC (if PFT not performed at visit)
- SHAQ-DI
- Physician Global Assessment
- Patient Global Assessment
- PFTs
- Complete PE

Page 51 of 99

- Vital signs
- Weight
- Hematology and chemistry
- Urinalysis
- 12-lead ECG
- Pregnancy test
- Collect and dispense study diary
- Study drug administration
- Collect study drug
- Concomitant medication assessment
- AE assessment

